- Tamibarotene/placebo will be administered at 6 mg twice per day (BID) (orally) each day on Days 8 through 28 of each 28-day treatment cycle.
- Azacitidine will be administered at 75 mg/m² (intravenously or subcutaneously) each day on Days 1 through 7 of each 28-day treatment cycle. If dosing on Days 6 and 7 is not possible due to logistical limitations, these doses may be delayed to Days 8 and 9. Tamibarotene/placebo is permitted to overlap with azacitidine on Days 8 through 9 of this alternative schedule.

Patients will receive treatment until they meet study drug discontinuation criteria, as described in the Overall Design. Patients will be followed until the number of OS events is sufficient to enable the final analysis.

Statistical Considerations

Statistical Hypotheses

Primary: CR Rate

Null hypothesis (H0): In RARA-positive patients with newly diagnosed HR-MDS, CR rate for patients in the tamibarotene plus azacitidine treatment group is the same as the CR rate for patients in the placebo plus azacitidine treatment group.

[figure not shown]
Alternative hypothesis (H1): In RARA-positive patients with newly diagnosed HR-MDS, CR rate for patients in the tamibarotene plus azacitidine treatment group is higher than the CR rate for patients in the placebo plus azacitidine treatment group.

Key Secondary: OS

Null hypothesis (H0): In RARA-positive patients with newly diagnosed HR-MDS, OS for patients in the tamibarotene plus azacitidine treatment group is the same as the OS for patients in the placebo plus azacitidine treatment group.

Alternative hypothesis (H1): In RARA-positive patients with newly diagnosed HR-MDS, OS for patients in the tamibarotene plus azacitidine treatment group is superior to the OS for patients in the placebo plus azacitidine treatment group.

Sample Size Determination

A total of cel death events will provide power to detect the difference in OS between the tamibarotene plus azacitidine treatment group and the placebo plus azacitidine treatment group, with assumed median survival of months versus months (hazard ratio = cel) in the 2 treatment groups, respectively, a 2:1 randomization, and 1-sided alpha of cel.

A total of approximately patients (in the tamibarotene plus azacitidine treatment group and c in the placebo plus azacitidine treatment group) are expected to be randomized in this study to obtain the death events and final analysis time at approximately 70 months.

Primary Endpoint Analysis

CR Rate

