6.5.1 Dose Delay and Toxicity-related Discontinuation Guidelines

If criteria for tamibarotene/placebo dose hold are met (Table 1), azacitidine dosing may continue, unless criteria for azacitidine hold are also met.

If criteria for azacitidine dose hold are met (Table 1), tamibarotene/placebo dosing may continue, unless criteria for tamibarotene/placebo hold are also met. Day 1 of the next treatment cycle is delayed until azacitidine dosing may resume.

If implementation of dose modification guidelines described in Table 1 (including dose holds and reductions) was not sufficient to adequately manage toxicity, the relevant study drug(s) should be discontinued. Discontinuation of only tamibarotene/placebo or only azacitidine while continuing administration of the other study drug may occur. If only azacitidine is permanently discontinued, Day 1 of the next treatment cycle may resume within 3 days of the decision to discontinue azacitidine.

If implementation of dose modifications described in Table 1 are insufficient to adequately manage toxicity and discontinuation of both tamibarotene/placebo and azacitidine is required, the patient should have an EoT Visit.

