7 DISCONTINUATION OF STUDY DRUG AND PATIENT DISCONTINUATION/WITHDRAWAL

7.1 Discontinuation of Study Drug Administration

Patients will continue to receive study drug until they meet one of the following criteria:

- An unacceptable toxicity, including AEs that would result in permanent discontinuation of study drug (Section 6.5)
- An AE related to study drug that requires ≥28 days (1 cycle) of dose interruption of both tamibarotene/placebo and azacitidine
- Failure to achieve a minimum response of HI in at least 1 cell lineage following the completion of the Cycle 7 Day 1 response assessment
- Disease progression/relapse
- Pregnancy
- Decision to pursue post-remission therapy (such as HSCT) or an alternative anticancer therapy; consolidation treatment with HSCT following the receipt of study drug is permissible.
- Patient withdraws consent for further study drug (interventional therapy) administration. The site should clarify with the patient if they maintain consent to follow up visits and calls after the end of study drug administration.
- Investigator determines it is in the best interest of the patient to discontinue study drug (interventional therapy) administration.

An EoT Visit should occur within 3 days of the last dose of study drug (or within 3 days of decision to permanently stop study drug treatment, if this decision directly follows a period when study drug has been on hold) and before the start of any subsequent anticancer therapy. A Safety Follow-up Visit should occur 30 days (\pm 3 days) after the EoT Visit and if possible before the start of any subsequent anticancer therapy. If the EoT Visit occurs \geq 30 days after the last dose of study drug, it may be combined with the Safety Follow-up Visit.

Patients will continue participation in all applicable follow-up assessments according to the SoA (Section 1.3).

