The number and percentage of patients with AEs or SAEs will be summarized. Laboratory values and changes in values from baseline will be summarized descriptively by visit, and shift tables will be provided showing change in National Cancer Institute (NCI) CTCAE (version 5) grade from baseline to worst grade postbaseline.

Laboratory Tests

Changes from baseline will be analyzed for each scheduled post-baseline visit for chemistry and hematology parameters. Where applicable, chemistry and hematology laboratory determinations will be categorized according to NCI CTCAE (Version 5) grades, and shift from baseline NCI CTCAE grades to worst post-baseline grades will be assessed.

Vital Signs

A shift from baseline to the worst post-baseline blood pressure category (normal to stage 2 hypertension) summary will be presented by treatment group and total according to each of the American College of Cardiology and American Heart Association 2017 guidelines.

Changes from baseline in systolic and diastolic blood pressure results will also be presented as box plots by visit and for each treatment group.

ECG

A shift from baseline category to the worst post-baseline category (Normal, Abnormal NCS, Abnormal CS) summary will be presented by treatment group and total. Prolonged QTcF intervals (>450 msec, >480 msec, and >500 msec) will be summarized by each visit. Change from baseline categories will also be summarized for measurements that represent a change >30 msec or >60 msec relative to the baseline value.

Change from baseline in QTcF interval results will also be presented as box plots by visit and for each treatment group.

All AE data, vital sign data and ECG data will be listed.

Additional details on the analyses will be provided in the SAP.

Table 4: Estimands (Secondary)

			Estimand Category		
Secondary Objectives	Treatment	Population	Variable/Endpoint	Intercurrent Event; Strategy	Population Level Summary

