6.3 Treatments

6.3.1 Treatments Administered

Study drug is defined as any investigational intervention(s), marketed product(s), or placebo intended to be administered to a participant according to the study protocol beginning on Cycle 1 Day 1.

Intervention Name	Tamibarotene	Tamibarotene-	Azacitidine
Type	Drug	Drug	Drug
Dose Formulation	Tablet	Tamibarotene- matched tablet	Reconstituted as solution or suspension
Unit Dose	2-mg tablets	Not applicable	100-mg single-use vials
Strength(s)			
Dosage Level and	6 mg BID; Days	3 tablets that	75 mg/m ² once per day;
D .	8 through 28 of	match	Days 1 through 7 of each
Regimen	each 28-day treatment cycle.	tamibarotene (BID); Days 8 through 28 of each 28-day treatment cycle	28-day treatment cycle. If dosing on Days 6 and 7 is not possible due to logistical limitations, these doses may be delayed to Days 8 and 9.
Route of Administration	Oral	Oral	Intravenous or subcutaneous
Use	Experimental	Placebo comparator	Background intervention

Table 2Study Treatments

Abbreviations: BID = twice per day

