7.3.10 Extent of Study Drug Exposure

The total number of cycles (maximum cycle reached) will be summarized using descriptive statistics for Safety Analysis Sets 1 and 2 by study drug (tamibarotene/placebo and azacitidine) and treatment group. Additionally, the number and percentage of participants will be summarized by the total number of cycles in which they were treated, according to the following categories: 1 to 2, 3 to 4, 5 to 6, and 7+ cycles.

For tamibarotene/placebo, actual and planned total dose, duration of exposure, and actual, planned, and relative dose intensity will be summarized using descriptive statistics for Safety Analysis Sets 1 and 2 by study drug.

• The duration of exposure in months will be calculated as

duration of exposure (months) = (date of last dose of tamibarotene/placebo – date of first dose of tamibarotene/placebo + 1) / 30.4375.

• Actual dose intensity in dose units (mg for tamibarotene/placebo) per month will be calculated as

actual dose intensity (mg/month) = total dose received (mg) / duration of exposure (months).

For the above actual dose intensity formula, the total dose received will be calculated in 2 steps:

1. Sum of the doses in each cycle (Cycle 1 (mg) = X1 dose, Cycle 2 (mg) = X2 dose, ... Cycle n (mg) = Xn dose);

2. Sum of non-zero dosing in all cycles (Cycle 1 (mg) + Cycle 2 (mg) + ... + Cycle n (mg)).

• Planned dose intensity in dose units (mg for tamibarotene/placebo) per month will be calculated as

planned dose intensity (mg/month) = planned total dose (mg) / duration of exposure (months).

Confidential

The planned total dose of tamibarotene and placebo will be calculated based on the total planned dose collected in the CRF up to EOT. For the above planned dose intensity formula, the planned total dose is the sum of the planned total doses in all cycles.

• Relative dose intensity for tamibarotene/placebo will be calculated as

relative dose intensity = actual dose intensity (mg/month) / planned dose intensity (mg/month).

For azacitidine, duration of exposure, total number of cycles of azacitidine, total number of doses, and average number of doses per cycle will be summarized using descriptive statistics for Safety Analysis Sets 1 and 2 by treatment group.

- Duration of treatment with azacitidine (months) = (date of last dose of azacitidine date of first dose of azacitidine + 1) / 30.4375.
- Total number of cycles will be calculated based on the maximum cycle reached.

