7.6.1 Adverse Events

Treatment-emergent adverse events (TEAEs) are defined as those AEs with onset after the first dose of study drug or existing events that worsened after the first dose during the study up until the last dose of study drug + 30 days. TEAEs will be summarized by treatment group. Selected TEAEs will also be summarized. The selected TEAEs include rash, pain, hypertriglyceridemia, venous thrombosis, anemia/RBC count decreased, thrombocytopenia/platelet count decreased, neutropenia/neutrophil count decreased, and leukopenia/white blood cell (WBC) count decreased. A detailed search strategy for the selected TEAE groups is provided in Appendix 1.

AEs with missing start and/or stop dates will be considered TEAEs. Imputation rules for partial and missing dates are described in Table 10.

Verbatim terms on CRFs will be mapped to PTs and SOCs using MedDRA, version 23.1 or higher. AEs will be graded using the National Cancer Institute (NCI) CTCAE version 5. If an AE grade is missing, the previous worst grade under the same PT will be assigned if it is available, otherwise a grade of 4 will be assigned for classification purposes in the TLFs.

The CTCAE Grade will be summarized by grouping Grade 1 and Grade 2 together, then Grade 3 and Grade 4 together, as well as Any Grade for all relevant TEAE tables.

Summaries of the following types will be presented by treatment group:

• Overall summary of the number of TEAEs, TEAEs by relationship to tamibarotene/placebo and azacitidine, TEAEs by CTCAE grade, serious AEs (SAEs), SAEs related to tamibarotene/placebo and azacitidine, selected TEAEs, TEAEs requiring concomitant medications, TEAEs leading to dose interruption of tamibarotene/placebo and azacitidine, TEAEs leading to dose reduction of tamibarotene/placebo and azacitidine, TEAEs leading to discontinuation of
tamibarotene/placebo and azacitidine, TEAEs leading to death (overall summary will also be analyzed based on mITT who received at least 1 study dose)

- TEAEs by SOC and PT
- TEAEs by PT
- TEAEs occurring in $\geq 10\%$ of participants in any treatment group by PT
- TEAEs related to tamibarotene/placebo by PT
- TEAEs related to azacitidine by PT
- TEAEs by CTCAE grade, SOC and PT
- TEAEs by CTCAE grade and PT
- TEAEs related to tamibarotene/placebo by CTCAE grade and PT
- TEAEs related to azacitidine by CTCAE grade and PT
- SAEs by SOC and PT
- SAEs by PT
- SAEs occurring in \geq 5% of participants in any treatment group by PT

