- SAEs related to tamibarotene/placebo by PT
- SAEs related to azacitidine by PT
- Selected TEAEs by PT
- Selected TEAEs related to tamibarotene/placebo by PT
- Selected TEAEs related to azacitidine by PT
- Selected TEAEs by PT and CTCAE grade
- Selected TEAEs related to tamibarotene/placebo by PT and CTCAE grade
- Selected TEAEs related to azacitidine by PT and CTCAE grade
- TEAEs requiring concomitant medications by PT
- TEAEs related to tamibarotene/placebo requiring concomitant medications by PT
- TEAEs related to azacitidine requiring concomitant medications by PT
- TEAEs leading to dose interruption of tamibarotene/placebo by PT
- TEAEs leading to dose interruption of azacitidine by PT
- TEAEs leading to dose reduction of tamibarotene/placebo by PT
- TEAEs leading to dose reduction of azacitidine by PT
- TEAEs leading to discontinuation of tamibarotene/placebo by PT
- TEAEs leading to discontinuation of azacitidine by PT

The overall summary of TEAEs will also be created for Safety Analysis Set 2, while all other safety outputs will be created only for Safety Analysis Set 1.

All deaths will be summarized based on the number and percentage of participants. This summary will classify participants by time of death relative to the last dose of treatment (>30 days or \leq 30 days) and analyze the primary cause of death. Off-treatment deaths (deaths occurring >30 days after the last dose of treatment) will only be summarized at the prespecified IA and the final OS analysis or based on a regulatory request.

Summaries by SOC and PT will be ordered by descending incidence of SOC and PT within each SOC based on the tamibarotene plus azacitidine group. Summaries by PT will be ordered by descending incidence of PT for the tamibarotene plus azacitidine group. At each level of summarization (e.g., any AE, SOC, and PT), participants experiencing more than 1 TEAE will be counted only once. In the summary of TEAEs by severity grade, participants will be counted once at the highest severity reported at each level of summarization; in the summary of TEAEs by relationship, participants will be counted once at the closest relationship to the indicated study drug (tamibarotene/placebo or azacitidine).

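### Adverse events are planned only as counts and crude percentages over a window set by time on any study drug; descriptive person-time and fixed-window tables would be a cheap supplement

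*SAP*

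**What the plan says.** **Measure.** Protocol 9.4.4 states: "The number and percentage of patients with AEs or SAEs will be summarized". SAP 7.6.1 lists tables by system organ class, preferred term (PT), grade and relationship, under the rule "At each level of summarization (e.g., any AE, SOC, and PT), participants experiencing more than 1 TEAE will be counted only once".

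**Window.** In SAP 7.6.1 a TEAE is an event starting after the first dose, or "existing events that worsened after the first dose during the study up until the last dose of study drug + 30 days". SAP 6.3.1 gives the meaning of study drug: "Study drug is defined as any investigational intervention(s), marketed product(s), or placebo intended to be administered to a participant". Its Table 2 includes azacitidine. Protocol 6.5.1 adds: "Discontinuation of only tamibarotene/placebo or only azacitidine while continuing administration of the other study drug may occur". Stopping tamibarotene/placebo alone therefore leaves the window open; it closes only after both drugs have stopped.

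**Duration of treatment.** Protocol 1.1: "Patients will receive treatment until they meet study drug discontinuation criteria, as described in the Overall Design". Besides toxicity and progression or relapse, Protocol 7.1 lists "Failure to achieve a minimum response of HI in at least 1 cell lineage following the completion of the Cycle 7 Day 1 response assessment" as a reason to stop.

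**Exposure.** SAP 7.3.10 gives one duration formula for tamibarotene/placebo and another for azacitidine; the azacitidine sentence begins "For azacitidine, duration of exposure, total number of cycles of azacitidine, total number of doses, and average number of doses per cycle". It also plans duration categories for study treatment, but gives no formula for time on either drug.

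**Not planned.** Neither document contains a person-time AE rate, a time-to-first-AE analysis or an AE table limited to a fixed period.

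**The concern.** Time at risk for a TEAE is itself an outcome after randomization, because response and tolerability determine it and treatment may change both. The crude percentage correctly answers what share of participants have the event over the treatment they actually receive. It does not show whether events occur faster on tamibarotene.

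The mixing can go either way. If more tamibarotene participants continue past Cycle 7, their percentages rise even at an equal event rate. If more of them stop both drugs early, a higher event rate can look nearly equal.

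The gap is mainly in serious adverse events (SAEs), general TEAE terms, and three of the eight selected groups: rash, pain and venous thrombosis. The other five are hypertriglyceridemia and the four blood-count groups, where the by-visit laboratory summaries in SAP 7.6.2 help.

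**Working it through.** The plan states no figure to reproduce. The documents as available give no AE rates, treatment durations or hematologic improvement (HI) rates by arm, so every rate below is an assumption.

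**Model.** Time on any study drug ends at hazard h0 per month until Cycle 7 Day 1. A share p reaches at least HI and continues with hazard h1; the rest stop there. The first-event hazard is λ.
- T = 168/30.4375 = 5.52 months (planned Cycle 7 Day 1 is Day 6 × 28 + 1 = 169).
- W = 30/30.4375 = 0.986 months.
- P(event) = 1 − exp(−λW) × [1 − λ(A + B)]
- A = [1 − exp(−(λ + h0)T)]/(λ + h0)
- B = p × exp(−(λ + h0)T)/(λ + h1)

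**Equal event rates, worked example.** λ = 0.03 in both arms, h0 = 0.05, h1 = 0.08, p = 0.75 v 0.55.
- exp(−0.08 × 5.52) = 0.643, so A = 0.357/0.08 = 4.46.
- B = 0.75 × 0.643/0.11 = 4.38 v 0.55 × 0.643/0.11 = 3.22.
- P = 1 − 0.971 × [1 − 0.03 × 8.85] = 28.7% v 1 − 0.971 × [1 − 0.03 × 7.68] = 25.3%.

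Onset through Day 169 is 14.0% in both arms, and the person-time rate ratio is 1.00.

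**Grid.** λ 0.01 to 0.05; h0 0.05 or 0.08; h1 0.08 or 0.12; p 0.70 v 0.60 or 0.75 v 0.55.
- Full follow-up: gap of 0.46 to 4.22 points.
- At a CR cut-off after an assumed 24 months of uniform accrual (follow-up 5.5 to 29.5 months): 0.30 to 2.76 points.
- Equal time on drug: 0.

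**Sampling error.** Taking the 190 patients of Protocol 9.4.2 at 2:1 (127 v 63), the 95% margin on the example is 1.96 × √(0.287 × 0.713/127 + 0.253 × 0.747/63) = 13.3 points. Safety Analysis Set 1 draws on all randomized participants, a number that is redacted, so this margin is only illustrative.

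**Larger exposure contrasts.** With exponential time on drug of median m, P = 1 − exp(−λW) × μ/(μ + λ), where μ = ln2/m. At equal λ, medians of 6 v 8 months give 16.4% v 20.3% (λ = 0.02); medians of 6 v 12 give 33.6% v 49.0% (λ = 0.05). Nothing in the documents supports contrasts of that size, but 4 points is not an upper limit.

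**Masking.** λ = 0.025 v 0.020 (true ratio 1.25), p = 0.60 in both arms, h1 = 0.08, early stopping of both drugs 0.10 v 0.05 per month.
- Crude 19.2% v 18.9%: ratio 1.01 (1.05 at the cut-off).
- Through Day 169, 10.9% v 9.6%: ratio 1.14. Person-time ratio 1.25.
- If 25, 50, 75 or 100% of the excess stopping is of tamibarotene only, the window stays open and the crude ratio is 1.05, 1.10, 1.15 or 1.20. This assumes the event rate is unchanged after tamibarotene stops.

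**Limits of the rate.** With identical hazards in both arms and the exposure of the worked example, the overall rate ratio is 0.91 (0.93 at the cut-off) for front-loaded events (0.10 per month for 2 months, then 0.01). It is 1.09 for late events (0.01 for 6 months, then 0.04). Split at Day 169, the ratios are 1.00 to 1.02.

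**Precision.** About 24 v 12 events around a ratio of 1.25 give factors exp(±1.96 × √(1/24 + 1/12)), or 0.63 to 2.5. For an assumed 5% event (0.05 × 127 = 6.35 v 0.05 × 63 = 3.15 expected), a ratio of 1 has an interval of about 0.26 to 3.9.

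**Reassignment.** SAP 7.2.3 counts tamibarotene-arm participants who stop before any tamibarotene dose in the placebo arm, and tamibarotene starts on Day 8. Suppose 4 of 127 move, all with an SAE, and the true SAE rate is 30% in both arms. The tables then show (0.30 × 63 + 4)/67 = 34.2% on placebo v (0.30 × 127 − 4)/123 = 27.7% on tamibarotene.

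**The case against.** The case against is strong, and most of it stands.

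- *Crude percentages are conventional and valid.* Correct. The counting rule has no defect.
- *The effect is small and assumed.* Also correct: 0.3 to 2.8 points at the cut-off against a margin of about 13. Noise does not remove a systematic shift, which can act on many terms in the same direction, but the size is modest.
- *Planned tables would show unequal stopping.* Largely correct. In the masking case exp(−0.10 × 5.52) = 58% v exp(−0.05 × 5.52) = 76% remain on drug at Cycle 7 Day 1. The cycle and duration categories (SAP 7.3.10), disposition (7.3.1) and TEAEs leading to discontinuation (7.6.1) would reveal most of that. They would not give event-free time by term, or a defined duration on either drug.
- *Such tables can be added later, and the data monitoring committee reviews safety regularly.* True, but SAP 4 gives avoiding post hoc choices as a purpose of the plan.
- *The remedy has its own faults.* It does. Rates for every SAE term would be too sparse. The reassignment rule gives the tamibarotene arm a period that its members must complete on treatment, and loads early stoppers onto placebo. AEs with missing dates count as TEAEs but may have no usable onset day. The fix has to deal with all three.

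A reader might also infer that a CR benefit will lengthen tamibarotene exposure and so inflate its AE percentages. The documents do not show this. The stopping rule depends on HI, not CR, and toxicity could shorten exposure instead.

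**Conclusion.** The point holds as a low-cost improvement. The AE tables are crude only, their window follows time on any study drug, and that time may differ by arm. On the main assumed grid, equal event rates give a gap of about 0.3 to 4 points, and none if exposure is equal. The size depends on the exposure contrast, which is not yet known.

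Two stronger readings are not supported. One is that the planned tables are wrong: they answer a legitimate question. The other is that the plan would hide tamibarotene toxicity: near-complete masking required the hazard of stopping both drugs to double, and it mostly disappears (crude ratio 1.20 against a true 1.25) when the excess stopping is of tamibarotene alone.

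**What to change.** In SAP 7.6.1, add two descriptive supplements for the overall TEAE and SAE summary and the selected TEAE groups, mainly rash, pain and venous thrombosis. Include individual SAE PTs only above a minimum frequency, such as the existing 5% table.

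1. Participants with a first event per 100 participant-months at risk, by arm, with 95% CI and number at risk. Time at risk runs from first dose to the earliest of first event, last dose of any study drug + 30 days, death or data cut-off. Show it overall and split at Day 169.
2. Number and percentage with onset through Day 169. Use a fixed day because cycles can be delayed (Protocol 6.5.1).

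Show both by randomized arm among dosed participants as well as by Safety Analysis Set 1, because of the SAP 7.2.3 reassignment. Report AEs with missing onset dates separately. In SAP 7.3.10, add duration on any study drug by arm. State that these tables supplement the crude percentages and do not replace them.

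**Cost.** A few tables from dates already collected, with no effect on alpha, power or data collection. The SAP should state the limits: overall rates assume a roughly constant hazard, stopping may be informative even within each period, intervals will be wide, and no ratio is to be read as a test.
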